Medications which have been re-started by the Investigator may be discontinued if in the Investigator's judgment the target IOP has been reached and the continued use of some or all of the therapy may not be required. Discontinuation of medications after re-introduction is recommended to be in the reverse order of re-introduction. The rationale for discontinuation will also be documented on the appropriate Follow-Up Visit Form by the Investigator. For medication discontinuation, the reason for the decision will be noted on the case report form such as IOP controlled, allergy to medication, or subject has undergone additional glaucoma surgery. A field for "Other" will be used to document any other reason for glaucoma medication discontinuation.

Another potential reason for intervention is an IOP below 6mmHg (hypotony). Interventions such as those indicated below should only be considered if the hypotony has caused or is likely to cause sequelae such as a flat chamber. No intervention is indicated when the vision is unchanged from the previous visit, there is no persistent choroidal detachment, the anterior chamber is not flat with lenscorneal touch, or the subject is asymptomatic. No intervention should be undertaken for hypotony which is not causing, or threatening to cause, a reduction in vision, as the intervention might cause procedure failure. These interventions should be documented as Adverse Events. Otherwise, the hypotony should be monitored with additional follow-ups as necessary.

- 1) Too loose or not enough sutures can result in hypotony that may be treated by adding more sutures in a separate surgical intervention (this action will be considered a failure).
- 2) Introduction of viscoelastic into the Anterior Chamber for the purpose of slowing aqueous flow and eliminating hypotony that is causing a reduction of best corrected visual acuity (two or more lines) or causing the presence of persistent choroidal detachment (3 or more months if peripheral, up to one month if kissing), or causing hypotony maculopathy (also documented on the Adverse Event Form as the action taken for an event.)

12. Adverse Events

An adverse event is any symptom, sign, illness, or experience, which develops or worsens during the course of the study, and which may or may not be considered device and/or procedure related.

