13.1. Anticipated Adverse Events

Anticipated adverse events include those that might reasonably be expected to occur in this study because they are associated with glaucoma, glaucoma surgery, and/or prior cataract surgical procedures. Specific examples of anticipated adverse events include:

- Hypotony; defined as IOP <6mmHg.
- 2. Increased intraocular pressure requiring medical or surgical intervention; Increased intraocular pressure will be considered an adverse event if a subject has an IOP higher than the preoperative medicated screening pressure or 21mmHg, whichever is lower. At this IOP level, the Investigator will intervene either physically or with the addition of glaucoma medication. There may also be cases where intervention for increased IOP is done at a lower IOP level than stated above because of other patient-related factors; these will also be adverse events.
- 3. Decrease of BCVA; BCVA decreases of 2 lines or more should not be reported as adverse events until they occur at two consecutive visits unless surgical or medical intervention is required. If the first decrease is noted at the Study Exit Visit, the subject will be exited and not brought back. In this case, the decrease will not be documented as an adverse event. (Note: a loss of BCVA in conjunction with posterior capsular opacification, followed by Nd:YAG capsulotomy and improvement of BCVA, is not considered an adverse event.)

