13.2. Post-operative Anticipated Adverse Events

- Anterior chamber puncture
- Aqueous humor misdirection (malignant glaucoma)
- Blebitis
- Bleb leak
- Bleb related complications e.g. cystic bleb, flat bleb
- Cataract progression
- Choroidal effusion/detachment
- Choroidal hemorrhage
- Chronic iritis
- Chronic pain

- · Clinically significant corneal damage
- Clinically significant iris damage
- Confirmed worsening in the visual field of mean deviation (MD) of ≥2.5 dB compared to the MD
 used to determine subject eligibility (confirmed on at least 2 out of 3 visual field tests performed
 after 3 months post procedure)
- Conjunctival dehiscence
- Conjunctival dissection
- Corneal abrasion
- Corneal edema
- Diplopia
- Device malfunction
- Encapsulated bleb
- Endophthalmitis
- Erosion of the device through the conjunctiva
- Event requiring unplanned glaucoma-related ocular surgical intervention
- Event requiring unplanned surgical intervention for reason other than glaucoma
- · Flat anterior chamber
- Hyphema at any time (including microhyphema)
- Hypotony (IOP<6mmHg at any time)
- Hypotony maculopathy
- Implant migration
- Increase in C/D ratio of ≥0.3 units on slit lamp biomicroscopic examination
- Increased IOP requiring treatment
- Leakage of wound site
- Loss of light perception
- Loss of 2 lines or more of BCVA on 2 consecutive follow-up visits
 (Note: a loss of BCVA in conjunction with posterior capsule opacification, followed by Nd:YAG capsulotomy and improvement of BCVA, is not considered an adverse event)
- Macular edema
- Optic disc hemorrhage
- Posterior capsule opacification
- Proptosis
- Ptosis
- Pupillary block
- Retinal complication (dialysis, flap tears, detachment, decompression or proliferative retinopathy)
- Shallow anterior chamber
- Strabismus
- Subconjunctival bleeding at any time
- Suture abscess or other local infection
- Tube obstruction, partial or complete, regardless of how long the obstruction is present
- Tube touching cornea
- Tube touching iris
- · Use of a viscoelastic to limit aqueous flow
- Vitreous hemorrhage

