14.2.4. Unanticipated Adverse Device Effects

All Unanticipated Adverse Device Effects (UADEs) will be reported to the study Sponsor, InnFocus, Inc. by email and/or telephone, and to the reviewing IRB/IEC as soon as possible but no later than 10 working days after the Investigator first learns of the event. The UADE should be documented in the EDC as a Serious Adverse Event using the Adverse Event Form. The date of event, its severity, treatment if any, and the assessed relationship of the event to the study device will be recorded on the Adverse Event form. The Sponsor will conduct an evaluation of all reported UADEs. The Sponsor shall report the results of such an evaluation to the FDA, and to all reviewing IRBs/IECs and participating investigators, within 10 working days after the Sponsor first receives notice of the effect. If the Sponsor determines that the UADE presents an unreasonable risk to subjects, the parts of the investigation presenting risk will be terminated. Termination will occur no later than 5 working days after the Sponsor makes such a determination and no later than 15 working days after the Sponsor first received notice of the effect.

Any UADEs involving a reoperation in the study eye, requiring the following should be documented on the Reoperation Form:

- a. Trabeculectomy
- b. Placement of a drainage device
- c. Bleb revision (other than needling)
- d. Explantation or repositioning of the PRESERFLO® MicroShunt
- e. Iridectomy
- f. Re-suturing of the scleral flap

The following procedures should be documented as the action taken for an Adverse Event:

- 1. Needling of the bleb with or without the use of an injected antifibrotic
- Laser removal of the blockage at the tip of the PRESERFLO® MicroShunt or at the anterior chamber entry point for a trabeculectomy
- 3. Use of a viscoelastic to limit aqueous flow

The following procedures should be documented as the action taken for an Adverse Event:

- Eye massage
- Laser suture lysis in a trabeculectomy

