9.2.2. Analysis of Secondary Safety Outcome Measures

9.2.2.1. Adverse Events

Subjects with any ocular AEs, SAEs, and UADEs will be tabulated and summarized by type of AEs for each study group. Ocular AE summaries (i.e., the number and percentage of subjects reporting to at least one AE) will also be provided for ocular AEs judged to be device- or procedure-related.

AEs, SAEs, and UADEs, if any, will be listed separately.

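### The protocol gives conflicting rules for recording hypotony and its treatment: an episode treated with viscoelastic is one or two AE types, and an untreated one may go unfiled

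*Protocol*

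**What the plan says.** Protocol 11.2 begins its hypotony paragraph with "Another potential reason for intervention is an IOP below 6mmHg (hypotony" and limits intervention to hypotony that has caused, or is likely to cause, sequelae. On recording it says "These interventions should be documented as Adverse Events. Otherwise, the hypotony should be monitored with additional follow-ups as necessary". Item 2 of the list below that paragraph deals with viscoelastic and has it "documented on the Adverse Event Form as the action taken for an event".

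Elsewhere in the protocol:

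- Section 13.1 gives as an anticipated AE "Hypotony; defined as IOP <6mmHg".
- Section 13.2 lists "Hypotony (IOP<6mmHg at any time" and, on a separate line, "Use of a viscoelastic to limit aqueous flow".
- Section 14.2.4 says "The following procedures should be documented as the action taken for an Adverse Event", and viscoelastic use is the third procedure on that list.
- Section 21.3 classes viscoelastic use as a complication and not a failure (SAP 8.1.5 agrees). Section 14.1 makes any complication an AE.

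The SAP counts from the AE records. Section 9.2.2.1 says "Subjects with any ocular AEs, SAEs, and UADEs will be tabulated and summarized by type of AEs for each study group".

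**The concern.** The same procedure is an event in some sections and a response to an event in others, so sites can file identical clinical facts differently while each follows the protocol. The 11.2 paragraph also attaches its AE instruction to interventions and then turns to monitoring for the rest. A coordinator working from that paragraph could conclude that untreated hypotony needs no AE form.

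Incidence of ocular AEs in the study eye is a listed secondary safety outcome, and the stated purpose of the study is long-term safety. The planned hypotony row comes from forms filed in an open-label study. If filing practice varies, that row partly reflects which section a site followed.

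**Working it through.** The documents state no hypotony rate, so there is no figure to reproduce. The check sets the sections side by side and counts the AE types each produces for one episode of IOP below 6 mmHg after consent.

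| Source | Untreated episode | Episode treated with viscoelastic |
|---|---|---|
| 11.2, main text | No AE instruction; monitoring only | 1: the intervention |
| 11.2 item 2, and 14.2.4 | Not addressed | 1: the event, with viscoelastic as the action taken |
| 13.1 | 1: hypotony | 1: hypotony; viscoelastic not mentioned |
| 13.2 | 1: hypotony | 2: hypotony and viscoelastic use |
| 21.3 with 14.1 | Not addressed | 2: viscoelastic use as a complication, hence an AE, besides hypotony |

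**Treated episode.** The count is one or two. Where it is one, the sections disagree on whether the record is the hypotony or the intervention. This conflict is explicit.

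**Untreated episode.** Sections 13.1 and 13.2 give one, with no condition about intervention. Section 11.2 is silent, and becomes zero only if monitoring is read as replacing the AE form.

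**Scope.** This applies after consent. For ocular AEs arising between Month 24 and consent, Protocol 13 asks for an AE record only where the event is ongoing and surgery, physical intervention or a medication change was required.

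**Effect on the tables.** SAP 9.2.2.1 counts subjects by AE type.

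- A subject filed under both hypotony and viscoelastic use appears in two rows but counts once among subjects with any ocular AE. Only by-type rows and listings change.
- A subject whose hypotony is not filed leaves the hypotony row. That subject also leaves the any-ocular-AE count if there is no other ocular AE.

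**Size.** Let u be the share of subjects with hypotony whose episodes all went untreated, and m the share of those left unfiled. Then

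reported hypotony rate / true rate = 1 − u × m.

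This runs from 1 (m = 0, nobody misreads) down to 1 − u (m = 1, everybody does). The documents give neither u nor m, nor any follow-up IOP distribution.

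**Would another planned output catch it?**

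- Coding before database lock (SAP 9.1.1) could merge duplicates, though no rule is given. It cannot restore an episode that was never filed.
- IOP summaries by visit (SAP 8.3.2) include a minimum but no count of low readings, and they drop IOP data for eyes with a glaucoma reoperation. Re-suturing the scleral flap is on that reoperation list (SAP 8.1.4.2.1), and item 1 of Protocol 11.2 names added sutures as a response to hypotony.
- The failure definition (SAP 8.1.5) counts IOP below 6 mmHg only when it is present on two consecutive visits.
- The SAP derives counts from measurements for visual acuity loss (9.2.2.2), endothelial cell density (9.2.2.3) and lens opacity (9.2.2.4). It has no such count for IOP below 6 mmHg.

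**The case against.** The strongest reply is that AE recording is governed by Protocol 12 to 14, not by a section on interventions. Section 12 counts untoward clinical signs as AEs. Section 13 requires ocular AEs after consent to be documented, with no intervention condition. Section 13.2 covers hypotony at any time. On this view 11.2 merely contrasts intervening with watching, and a site that files nothing breaches 13.1 and 13.2. This stands. A reader might infer that 11.2 exempts untreated hypotony from AE recording, but no passage says so; the text only invites the misreading. Nor does any one episode span zero, one and two records: untreated and treated episodes are separate cases.

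The reply also holds on consequences. An extra viscoelastic row does not alter the hypotony row. Low IOP is not wholly hidden either, because individual data are listed (SAP 5) and persistent low IOP is a failure category. A reader might go further and infer a biased contrast between arms because investigators are unmasked. The documents do not show that: nothing suggests that a site would follow one section for MicroShunt and another for trabeculectomy.

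The reply does not remove the explicit event-or-action conflict for treated episodes, or the absence of any count of eyes with a reading below 6 mmHg.

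**Conclusion.** The concern holds in a limited form. The recording rules for viscoelastic use contradict one another, so a treated episode is one or two AE types. An untreated episode after consent is one AE under 13.1 and 13.2, with a real risk that 11.2 leads a site to file none.

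Double recording affects by-type rows and listings only. Non-recording would lower the hypotony rate and could lower the share of subjects with any ocular AE. The amount cannot be estimated from the documents, and any percentage would only restate an assumed share of untreated episodes and an assumed rate of misreading. The primary outcome, sight-threatening AEs, is not affected by this wording. The change is worth making because it is small and hypotony can be counted from readings the study already takes.

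**What to change.** **Protocol (recording only; no change to when anyone intervenes).** Reconcile 11.2 (main text and item 2), 13.2, 14.1, 14.2.4 and 21.3 on one rule. After consent, each episode of IOP below 6 mmHg is recorded once as the AE hypotony and followed to resolution, and any intervention is entered as the action taken. Wording the rule by episode avoids logging one persistent episode at every visit. Deleting the viscoelastic line from 13.2 is not enough, because 21.3 with 14.1 would still make it an AE. Leave the Month 24-to-consent rule in Section 13 as it is.

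**SAP 9.2.2.1.** Add, per arm, the number and percentage of study eyes with any recorded IOP below 6 mmHg at a scheduled visit, with the number of eyes measured as denominator. Do not apply the effectiveness censoring. Give the arm difference and exact 95% confidence intervals by the methods of SAP 9.2.1 (Clopper-Pearson for each arm, Chan-Zhang for the difference). Show unscheduled readings separately, since no assessment is required at those visits and measurement there is discretionary.

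**Cost.** The protocol wording needs amendment review and approval (Protocol 18.11), and the reported hypotony rate may rise. The SAP table needs no new data. It can be added on its own even if site records cannot be corrected, and its scheduled-visit count does not depend on which section a site followed.

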13.1. Anticipated Adverse Events

Anticipated adverse events include those that might reasonably be expected to occur in this study because they are associated with glaucoma, glaucoma surgery, and/or prior cataract surgical procedures. Specific examples of anticipated adverse events include:

- Hypotony; defined as IOP <6mmHg.
- 2. Increased intraocular pressure requiring medical or surgical intervention; Increased intraocular pressure will be considered an adverse event if a subject has an IOP higher than the preoperative medicated screening pressure or 21mmHg, whichever is lower. At this IOP level, the Investigator will intervene either physically or with the addition of glaucoma medication. There may also be cases where intervention for increased IOP is done at a lower IOP level than stated above because of other patient-related factors; these will also be adverse events.
- 3. Decrease of BCVA; BCVA decreases of 2 lines or more should not be reported as adverse events until they occur at two consecutive visits unless surgical or medical intervention is required. If the first decrease is noted at the Study Exit Visit, the subject will be exited and not brought back. In this case, the decrease will not be documented as an adverse event. (Note: a loss of BCVA in conjunction with posterior capsular opacification, followed by Nd:YAG capsulotomy and improvement of BCVA, is not considered an adverse event.)

13.2. Post-operative Anticipated Adverse Events

- Anterior chamber puncture
- Aqueous humor misdirection (malignant glaucoma)
- Blebitis
- Bleb leak
- Bleb related complications e.g. cystic bleb, flat bleb
- Cataract progression
- Choroidal effusion/detachment
- Choroidal hemorrhage
- Chronic iritis
- Chronic pain

- · Clinically significant corneal damage
- Clinically significant iris damage
- Confirmed worsening in the visual field of mean deviation (MD) of ≥2.5 dB compared to the MD
 used to determine subject eligibility (confirmed on at least 2 out of 3 visual field tests performed
 after 3 months post procedure)
- Conjunctival dehiscence
- Conjunctival dissection
- Corneal abrasion
- Corneal edema
- Diplopia
- Device malfunction
- Encapsulated bleb
- Endophthalmitis
- Erosion of the device through the conjunctiva
- Event requiring unplanned glaucoma-related ocular surgical intervention
- Event requiring unplanned surgical intervention for reason other than glaucoma
- · Flat anterior chamber
- Hyphema at any time (including microhyphema)
- Hypotony (IOP<6mmHg at any time)
- Hypotony maculopathy
- Implant migration
- Increase in C/D ratio of ≥0.3 units on slit lamp biomicroscopic examination
- Increased IOP requiring treatment
- Leakage of wound site
- Loss of light perception
- Loss of 2 lines or more of BCVA on 2 consecutive follow-up visits
 (Note: a loss of BCVA in conjunction with posterior capsule opacification, followed by Nd:YAG capsulotomy and improvement of BCVA, is not considered an adverse event)
- Macular edema
- Optic disc hemorrhage
- Posterior capsule opacification
- Proptosis
- Ptosis
- Pupillary block
- Retinal complication (dialysis, flap tears, detachment, decompression or proliferative retinopathy)
- Shallow anterior chamber
- Strabismus
- Subconjunctival bleeding at any time
- Suture abscess or other local infection
- Tube obstruction, partial or complete, regardless of how long the obstruction is present
- Tube touching cornea
- Tube touching iris
- · Use of a viscoelastic to limit aqueous flow
- Vitreous hemorrhage

13.3. Sight-Threatening Anticipated Adverse Events

Sight-threatening Adverse Events include, but are not limited to, events such as:

- 1. Endophthalmitis
- Corneal decompensation
- 3. Severe retinal detachment
- 4. Severe choroidal hemorrhage
- 5. Severe choroidal detachment
- 6. Aqueous misdirection

Adverse Event Reporting

14.1. Safety Reporting Information Requirements

Each subject will be carefully evaluated by the Investigator for Adverse Events. Any complication occurring, whether or not related to the device, will be considered an Adverse Event and will be recorded on the Adverse Event Form. The Investigator will document the Adverse Event's severity classification and relationship to the device and procedure on the Form. The following Adverse Event attributes must be assigned by the Principal Investigator:

- Adverse event (diagnosis if known, signs and symptoms if not known)
- Date of onset
- Date of resolution
- Outcome
- Severity
- Relationship to the device and/or device explantation procedure

Assessment of Severity:

The description of the severity of the adverse event on the Adverse Event Form should use the following scale:

Mild: Any event that results in minimal transient impairment of body function or damage to a body structure, and does not require intervention other than monitoring

Moderate: Any event that results in moderate transient impairment of body function or damage to a body structure, or requires intervention to prevent permanent impairment of body function or damage to a body structure

Severe: Any event which is life threatening, which results in permanent impairment of a body function or damage to a body structure, or which requires significant intervention (e.g., a major surgery), to prevent permanent impairment of a body function or damage to a body structure.

Assessment of Relatedness:

All Adverse Events will be classified by the Principal Investigator with respect to attribution of causality according to the following classifications:

Device Related:

An adverse event that is directly related to the use, presence and/or performance of the PRESERFLO® MicroShunt.

Procedure Related:

An adverse event that is directly related to the initial study surgical procedure (PRESERFLO® MicroShunt, Trabeculectomy, or general surgical complications).

Not related:

The adverse event was not caused by the device, its explantation, or the procedure.

- Definite: Follows a reasonable temporal sequence from device delivery/retrieval and cannot be reasonably explained by known characteristics of the subject's clinical data or the surgical procedure applied.
- Probable: Follows a reasonable temporal sequence from device delivery/retrieval that
 is unlikely to have been produced by the subject's clinical state or by the surgical
 procedures regardless of the device.
- Uncertain: Follows a reasonable temporal sequence from device delivery/retrieval but could have been produced by the subject's clinical state or by the surgical procedures regardless of the device
- None: Temporal association is such that the device is not likely to have had any
 reasonable association with the observed event.

14.2. Adverse Event Reporting Procedures

All Adverse Events should be documented in the EDC by completing the Adverse Event Form and, if applicable, an IRB/IEC-specific form. Identification and collection of adverse event information will be the joint responsibility of the study Sponsor, the CRO, and the study investigators. The Sponsor, Investigator, and the CRO will all follow the Declaration of Helsinki in order to ensure the safety of all subjects.

